8.4.3 Data Collected at Study Completion

For patients who complete the observation period, the study completion visit should be documented.

Please see Appendix 2 for the data collection overview at the study completion visit if available.

8.4.4 Data Collected during Follow-Up

After the study completion visit, adverse events (AEs) should be followed as outlined in Section 10.1.4.2.

Please see Appendix 2 for the data collection overview during follow-up.

8.4.5 Safety Data Collection

Clinical AEs, serious and non-serious, as well as safety data other than AEs as described in Section 8.3 will be recorded in the CRF during the total observation period. For clinical AEs, serious and non-serious, physician's assessment of severity (mild, moderate, severe or in oncology studies using the National Cancer Institute [NCI] Common Terminology Criteria for Adverse Events [CTCAE]) and relationship to therapy (i.e., related or unrelated) will be recorded as described in Appendix 3.

8.5 STUDY SIZE

In this study 225 patients will be enrolled across 40 sites.

The following rates are expected for the two different populations:

- Cohort A: patients with AJCC stage IIIC unresectable and stage IVa, b, c mM without cerebral metastases: 70% (157 patients)
- Cohort B: patients with AJCC stage IVC and cerebral metastases: 30% (68 patients)

The required sample size was estimated for Cohort B (brain metastases) and Cohort A (non-brain metastases). For the brain metastases group, a historical median OS of about 8 months is assumed under vemurafenib treatment (1-4). The aim was to find the required number of patients in order to estimate the median OS in such a way that the lower limit of the 95% confidence interval is at least 8 months. If a median OS of 12 months is assumed, a one-sample non-parametric survival analysis would yield in a confidence interval of [8.5 months ; 15.5 months], given the sample size was 68 (10% dropout rate included). For the non-brain metastases group, the aim was to set the number of patients in such a manner that the lower boundary of its associated median OS confidence interval does not overlap with the upper boundary of the brain metastasis group. If a median OS of 25 months is assumed, the 95% confidence interval for the median OS is [19; 31] months (5).

8.6 DATA MANAGEMENT

8.6.1 Data Quality Assurance

A contract research organization (CRO) will be responsible for data management of this study, including quality checking of the data. Data entered manually will be collected via EDC using CRFs. Sites will be responsible for data entry into the EDC system. In the event of discrepant data, the CRO will request data clarification from the sites, which the sites will resolve electronically in the EDC system.

The CRO will produce a Data Quality Review Plan that describes the quality checking to be performed on the data.

The marketing authorization holder will perform oversight of the data management of this study, including approval of the CRO data management plans and guidance (including Data Quality Review Plan). Data will be periodically transferred electronically from the CRO to the marketing authorization holder, and the CRO's standard procedures will be used to handle and process the electronic transfer of these data.

CRFs and correction documentation will be maintained in the EDC system audit trail. System backups for data stored at the CRO and records retention for the study data will be consistent with the CRO standard procedures. The CRO will comply with the MAH's procedures regarding archiving and record management

8.6.2 Electronic Case Report Forms

CRFs are to be completed using a marketing authorization holder-designated electronic data capture (EDC) system. Sites will receive training and have access to a manual for appropriate CRF completion. CRFs will be submitted electronically to the marketing authorization holder and should be handled in accordance with instructions from the marketing authorization holder.

All CRFs should be completed by designated trained site staff. CRFs should be reviewed and electronically signed and dated by the physician or a designee.

At the end of the study, the physician will receive the data related to patients from his or her site in an electronically readable format (e.g., on a compact disc). Data must be kept with the study records. Acknowledgement of receipt of the data is required.

8.6.3 Source Data Documentation

Site Operations Representative will perform ongoing SDV as defined in the Trial Monitoring Plan to confirm that critical protocol data (i.e., source data) entered in the

CRF by authorized site personnel are accurate, complete, and verifiable from source documents.

Source documents (paper or electronic) are those in which patient data are recorded and documented for the first time. They include, but are not limited to, hospital records, clinical and office charts, laboratory notes, memoranda, PROs, evaluation checklists, pharmacy dispensing records, recorded data from automated instruments, copies of transcriptions that are certified after verification as being accurate and complete, microfiche, photographic negatives, microfilm or magnetic media, X-rays, patient files, and records kept at pharmacies, laboratories, and medico-technical departments involved in a clinical study.

Before study initiation, the types of source documents that contain study-relevant information will be clearly defined in the Trial Monitoring Plan. The Trial monitoring plan defines which kind of source data – if available from clinical routine - can be used for documentation into CRF. No additional source data creation beyond routine is allowed.

Source documents that are required to verify the validity and completeness of data entered in the CRF must not be obliterated or destroyed and must be retained per the policy for retention of records described in Section 8.6.5.

To facilitate SDV, the physicians and institutions must provide the marketing authorization holder direct access to applicable source documents and reports for study-related monitoring, marketing authorization holder audits, and IRB/EC review. The participating sites must also allow inspection by applicable health authorities.

8.7 DATA ANALYSIS

No statistical model will be used in the efficacy analysis and no formal hypothesis testing is planned. All effectiveness and safety variables documented in this study will be analyzed by means of descriptive analyses.

Continuous data will be summarized using mean, standard deviation, median, minimum and maximum. Categorical variables will be expressed as absolute and relative number and 95% CI. Kaplan-Meier estimates and Cox-regression will be used to model data on time to disease progression and OS.

Definition of core analysis population

Analyses will include all patients who received at least one dose of cobimetinib and vemurafenib.

A data review meeting to designate patients to the different populations will be held before database closure.

8.7.1 Safety Analyses

All patients who received at least once cobimetinib and vemurafenib will be part of the safety population which is identical to the core analysis population.

The analysis of safety outcomes/variables is based on the incidence and severity of all AEs, SAEs, AEs with NCI CTCAE version {4.0}.

Safety will be assessed through summaries of adverse events. Descriptive statistics will be used to summarize all safety data. Adverse event data will be reported in listings and presented in frequency tables by Medical Dictionary for Regulatory Affairs (MedDRA) terms. All adverse events occurring after treatment will be summarized. Summaries of adverse events by grade, seriousness, and relationship to study treatment will be presented, as well as summaries of adverse events leading to death or to premature withdrawal from study treatment. Serious adverse events, including deaths, will be listed separately and summarized.

8.7.2 Effectiveness Analyses Effectiveness analyses will be based on all enrolled patients according to both defined cohorts:

Patients with:

Cohort A: patients with AJCC stage IIIC unresectable and stage IVA, B, C mM without cerebral metastases

or

Cohort B: patients with AJCC stage IVC and cerebral metastases

All effectiveness and variables documented in this study will be analyzed by means of descriptive analyses.

Continuous data will be summarized using mean, standard deviation, median, minimum and maximum. Categorical variables will be expressed as absolute and relative number and 95% CI. Kaplan-Meier estimates and Cox-regression will be used to model data on time to disease progression and OS.

All efficacy analyses will be performed separately for both groups.

The primary variable OS is defined as time interval from study start to death for any cause. Patients who have not died will be censored at the last date the patient was known to be alive. A 95% confidence interval will be calculated for the median overall survival.

PFS is defined as the interval between the start date of treatment and the date of progression or death for any cause, whichever comes first. Patients who have neither progressed nor died will be censored on the date of last evaluable tumor assessment.

Patients who had no post-baseline assessments and did not have an event will be censored OR is defined as a complete or a partial response documentation on the basis of investigator assessment.

Time to CNS relapse is defined as the interval between start date of treatment and the date of CNS relapse or death for any cause, whichever comes first.

PRO analyses, as measured by EORTC QLQ-C30, will be evaluated for patients with a baseline assessment and at least one post-baseline QLQ-C30 assessment that generate a score. Total QLQ-C30, each domain score (e.g., physical functioning, role functioning, emotional functioning, cognitive functioning, social functioning), as well as symptom scales, will be examined at baseline, and change from baseline for each timepoint by use of descriptive statistics.

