8. RESEARCH METHODS

8.1 STUDY DESIGN

[figure not shown]
This multi-center, two cohort non-interventional study does not influence the individually selected treatment scheme. The physicians' choice for a particular type of therapy is not influenced. Only documentation of the chosen therapy is part of this study. Data collection during therapy with cobimetinib / vemurafenib should reflect clinical routine. Overall, the duration of patient inclusion will last until end of Q4 2018.

- Patients with:

Cohort A: 157 patients with AJCC stage IIIC unresectable and stage IVA, B, C mM without cerebral metastases

or

Cohort B: 68 patients with AJCC stage IVC and cerebral metastases may be included

Start Date of Study:

The study start date will be the date of the first data collection: the date from which information on the first study subject is recorded in the study database. The planned start date is Q2/2017.

End of Study:

The end of the study will be the date from which the last information of the last subject is recorded in the study database. The planned end of study date is Q2/2020.

Length of Study

This study will last for 3 years. Patients will be recruited for 18 months and followed up to 18 months.

A data collection overview is provided in Appendix 2.

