8.2.2 Study Population

Patients receiving treatment for BRAF V600-mutated unresectable or metastatic mM with a combination of vemurafenib and cobimetinib according to standard of care and in line with the current summary of product characteristics (SmPC)/local labeling and who have no contraindication to a treatment with a combination of vemurafenib and cobimetinib therapy as per the local label are eligible for observation in this non interventional study if the following criteria applies.

Patients must meet the following criteria for study entry:

- Adult patients with unresectable or metastatic melanoma with a BRAF V600 mutation according to SmPC
- Be willing and able to provide informed consent for the non-interventional study.
- Male or female patient being ≥ 18 years of age on day of signing informed consent.
- Histologically confirmed diagnosis of unresectable or metastatic mM (according to the cobimetinib label)
- Presence of BRAF mutation (V600) in tumor tissue prior to enrolment.

Patients who meet any of the following criteria will be excluded from study entry:

- Previous treatment with BRAF- and/or MEK inhibitors prior to study entry
- Hypersensitivity to the active substances or to any of the excipients listed in appendix 4.

Patient selection criteria are as broad as mentioned in the SmPC, with one exception: Patients previously treated with BRAF- and/or MEK inhibitors are excluded. This may lower the number of patients available for recruitment in a further line setting.

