8.3 VARIABLES

8.3.1 Primary Variable

The primary variable for this study is as follows:

- OS: Time interval between start of treatment and date of death for any cause

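### Section 8.7.2 counts the primary endpoint OS from study start, contradicting the treatment-start origin in section 8.3.1

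*Protocol*

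**What the plan says.** **Time origin of OS.** The variables section (8.3.1) reads: "OS: Time interval between start of treatment and date of death for any cause". The effectiveness analysis section (8.7.2) reads: "The primary variable OS is defined as time interval from study start to death for any cause".

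**Meaning of study start.** Section 8.1 gives the only definition: "The study start date will be the date of the first data collection", which it explains as "the date from which information on the first study subject is recorded in the study database". The synopsis repeats this. It is a single calendar date shared by all patients.

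**Other time-to-event variables.** In 8.7.2, PFS and time to CNS relapse both run from the start date of treatment.

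**Analysis set.** Section 8.7 says: "Analyses will include all patients who received at least one dose of cobimetinib and vemurafenib". Section 8.7.2 says: "Effectiveness analyses will be based on all enrolled patients according to both defined cohorts". The synopsis carries both statements.

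**The concern.** The primary endpoint has two different clocks, and the one in the analysis section is a defined term that does not belong to the individual patient. A patient recruited in month 15 who dies 6 months after first dose would have an OS of 21 months by 8.7.2 and 6 months by 8.3.1. OS would also be the only time-to-event variable not counted from treatment start, so it could not be set beside PFS.

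At stake are the median OS in each cohort and its confidence interval, which are the main results of the study, and any reading of the brain-metastasis cohort against the 8-month historical figure in 8.5.

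The analysis set is a smaller matter with a link to the first. If effectiveness covers all enrolled patients, a patient who never received the drugs has no OS origin under 8.3.1 and no PFS origin under 8.7.2.

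**Working it through.** **Inputs from the protocol**
- Section 8.1: "Patients will be recruited for 18 months and followed up to 18 months".
- Section 8.5, cohort B (brain metastases): n = 68 with 10% dropout included; historical median 8 months; assumed median 12 months; stated 95% CI [8.5; 15.5]; aim of a lower limit of at least 8 months.
- Sections 8.1 and 8.5, cohort A (no brain metastases): n = 157; assumed median 25 months; stated 95% CI [19; 31].

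**Assumptions not in the protocol:** exponential survival and uniform accrual, with first dose at recruitment unless stated otherwise.

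**Step 1: the plan's own intervals.** Use m ± 1.96·m/√d, where d = n·(1 − 2^(−18/m)) is the expected number of deaths with 18 months of follow-up per patient.
- Cohort B: d = 68 × (1 − 0.354) = 44.0; 12 ± 1.96 × 12/√44.0 = [8.45; 15.55]. Stated: [8.5; 15.5].
- Cohort A: d = 157 × (1 − 0.607) = 61.7; 25 ± 1.96 × 25/√61.7 = [18.8; 31.2]. Stated: [19; 31].

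Taking off 10% dropout and using 18 months of accrual plus 18 months of further follow-up gives nearly the same: B [8.6; 15.4] from 47.6 events, A [19.3; 30.7] from 73.6 events. The sample size is therefore consistent with a clock that starts separately for each patient.

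**Step 2: literal study-start origin.** OS becomes T + E, where T is survival from first dose and E is the wait from study start to first dose, uniform on 0 to 18 months (mean 9). With λ = ln 2/m, setting P(T + E > t) = 0.5 gives, for t > 18,

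t = (1/λ) · ln[ 2(e^(18λ) − 1)/(18λ) ].

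| True median | 18λ | e^(18λ) | Median from study start |
|---|---|---|---|
| 8 | 1.560 | 4.757 | 18.1 |
| 12 | 1.040 | 2.828 | 21.8 |
| 25 | 0.499 | 1.647 | 34.4 |

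**Step 3: what an analysis would show.** Simulated Kaplan-Meier analyses (2,000 runs per case, Brookmeyer-Crowley limits, 10% dropout at a uniform random time, follow-up to month 36) give these typical results:

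| Case | From treatment start | From study start |
|---|---|---|
| B, true median 8 | 7.9 [5.6; 11.1] | 18.2 [15.6; 21.4] |
| B, true median 12 | 11.9 [8.4; 16.6] | 21.8 [18.3; 26.5] |
| A, true median 25 | 25.1 [19.9; 34.0] | 34.5 [29.2; not reached] |

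For cohort A the upper limit was not reached in about 47% of runs from treatment start and about 91% from study start. If the true cohort B median were only the historical 8 months, the lower limit would be at least 8 in all runs from study start, against about 3% from treatment start.

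**Step 4: study start read as each patient's study entry.** Suppose entry precedes first dose by a time uniform on 0 to D months (D is assumed; the protocol gives no figure). The Step 2 formula with D in place of 18 gives, for a true 12-month median:
- D = 1: 12.5 months
- D = 3: 13.5 months
- D = 6: 15.1 months

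If entry followed first dose, each patient's OS from entry would be shorter than OS from first dose by that lag.

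**The case against.** The strongest reply is that *study start* in 8.7.2 is a loose phrase. Section 8.3.1 states the treatment-start origin plainly, PFS and CNS relapse use it, and the sample-size intervals reproduce with a per-patient clock. A programmer working from a separate SAP might never apply the calendar date. This stands as an argument about intent, and it makes the shift of 9 to 10 months the extreme case. It does not remove the contradiction: 8.7.2 uses a term that the protocol defines, and defines otherwise.

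It is also fair to say that 8 months is a precision aim used to size cohort B. Section 8.7 plans no formal hypothesis testing, so no success rule would be falsely met. What would be lost is the meaning of that aim.

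On the analysis set, 8.2.2 limits eligibility to "Patients receiving treatment for BRAF V600-mutated unresectable or metastatic mM with a combination of vemurafenib and cobimetinib", so enrolled patients without a dose of both drugs should be few. A data review meeting before database closure is to assign patients to populations. Both points make the conflict minor, but the meeting cannot apply a definition that is given in two ways.

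Two stronger readings are tempting. A reader might infer that every departure from treatment start lengthens OS. That is not so: entry after first dose would shorten OS counted from entry. A reader might also infer immortal-time bias from the wording about patients receiving treatment, since 9.3 requires consent only before data are documented. But 8.2.2 also excludes BRAF or MEK inhibitor treatment before study entry, which read literally bars entry after first dose, and no passage gives a lag. The documents do not support that claim.

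**Conclusion.** The point holds as a contradiction in the definition of the primary endpoint. Sections 8.3.1 and 8.7.2 cannot both be applied, and 8.7.2 is the one out of line with the rest of the protocol.

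The size depends on the reading. Under the protocol's own definition of study start, medians rise by about 9 to 10 months (12 to 21.8; 25 to 34.4), given exponential survival and uniform 18-month accrual. Read as study entry before first dose, a 12-month median moves by about 0.5 to 3.1 months for assumed lags of up to 1 to 6 months. With entry after first dose the direction reverses. Upward bias is certain only under the literal reading.

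The conflict over the effectiveness set is real but secondary, and its size cannot be derived from the protocol. It should be corrected before analysis because it concerns the primary variable and costs very little.

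**What to change.** In 8.7.2, define OS as the time from start of cobimetinib/vemurafenib treatment to death from any cause, matching 8.3.1, PFS and time to CNS relapse. The existing censoring rule can stay.

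As a secondary change, name one effectiveness set in 8.7, 8.7.2 and the synopsis: enrolled patients with at least one dose of both drugs. Report enrolled but undosed patients in the disposition table.

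The cost is one sentence for the origin and a few words in three places for the set. The treatment start date is already collected at baseline (8.4.2 and Appendix 2), so no new data are needed. The sample size is unaffected, since its intervals are consistent with a per-patient clock.

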8.7.3 Interim/Final Analysis and Timing of Analyses

An interim analysis is not planned.

At the end of the study the date from which the last information of the last subject is recorded in the study database the final analysis will be done.

8.8 QUALITY CONTROL

8.8.1 Study Documentation

The physician must maintain adequate and accurate records to enable the conduct of the study to be fully documented, including but not limited to the protocol, protocol amendments, Informed Consent Forms, and documentation of IRB/EC and governmental notification. In addition, at the end of the study, the physician will receive

the patient data, which include an audit trail containing a complete record of all changes to data.

The Marketing Authorization Holder shall ensure that the dataset and statistical programs used for generating the data included in the final study report are kept in electronic format and are available for auditing and inspection.

8.8.2 Use of Site Computerized Systems

When clinical observations are entered directly into a participating site's computerized medical record system (i.e., in lieu of original hardcopy records), the electronic record can serve as the source document if the system has been validated in accordance with health authority requirements pertaining to computerized systems used in clinical research. An acceptable computerized data collection system allows preservation of the original entry of data. If original data are modified, the system should maintain a viewable audit trail that shows the original data as well as the reason for the change, name of the person making the change, and date of the change.

8.8.3 Retention of Records

Records and documents pertaining to the conduct of this study, including CRFs and Informed Consent Forms, must be retained by the physician for at least 15 years after completion or discontinuation of the study, or for the length of time required by relevant national or local health authorities, whichever is longer. After that period of time, the documents may be destroyed, subject to local regulations.

No records may be disposed of without the written approval of the marketing authorization holder. Written notification should be provided to the marketing authorization holder prior to transferring any records to another party or moving them to another location.

All supporting functional parties will comply with the MAH procedures regarding archiving and record management.

8.8.4 Site Audits and Inspections

Site visits will be conducted by the marketing authorization holder or an authorized representative for audit of study data, patients' medical records, and CRFs.

The physician will also permit national and local health authorities to inspect facilities and records relevant to this study.

